#### Duration of Stable Disease

Stable disease is measured from the start of the treatment (in randomized trials, from date of randomization) until the criteria for progression are met, taking as reference the smallest sum on study (if the baseline sum is the smallest, this is the reference for calculation of PD).

The clinical relevance of the duration of stable disease varies in different studies and diseases. If the proportion of subjects achieving stable disease for a minimum period of time is an endpoint of importance in a particular trial, the protocol should specify the minimal time interval required between two measurements for determination of stable disease.

Note: The duration of response and stable disease as well as the progression-free survival are influenced by the frequency of follow-up after baseline evaluation. It is not in the scope of this guideline to define a standard follow-up frequency. The frequency should take into account many parameters including disease types and stages, treatment periodicity, and standard practice. However, these limitations of the precision of the measured endpoint should be taken into account if comparisons between trials are to be made.

# 14.3. APPENDIX 3: GUIDANCE FOR IMMUNE-RELATED ADVERSE REACTIONS MANAGEMEMT

Identification, diagnosis, management of immune-related adverse events and dose adjustment method are listed in detail as following:

irAE	Potential signs and symptoms	Diagnosis and differential diagnosis	Recommended management	Dose modification
Pneumonitis	Symptomatic : dyspnea, cough, pleuritic chest pain, hypoxia Asymptomati c: lung infiltrates that mimic severe bacterial pneumonia	
 
Radiographic imaging of chest
 
Observe the specimen of tissues and lavage fluids used in bronchoscopy to investigate infectious pathogens and perform a pathologic evaluations on them
 
	Moderate (Grade 2): administration of corticosteroids at a dose of 1-2 mg/kg/day prednisone equivalents Severe (≥ Grade 3): high dose corticosteroids (2-4 mg/kg/day IV methylprednisolone) along with antibiotics; in-patient hospitalization; consultation with a respiratory physician; additional immunosuppression with infliximab can be considered	Withhold the administration of CS10 until resolved to ≤ Grade 1 Permanent discontinuation from the study
Colitis	Watery diarrhea, mucus or blood in stool, abdominal pain, nausea/vomiti ng, dehydration, peritoneal signs, bowel perforation	
 
Stool cultures
 
Endoscopy or colonoscopy to rule out infection
 
Biopsy to rule out alternative etiology
 
	Moderate (≤Grade 2) diarrhea: antidiarrheal medication, oral hydration, electrolyte supplement Persistent Moderate (Grade 2) diarrhea: administration of corticosteroids at a dose of 1-2 mg/kg/day prednisone equivalents Severe (Grade 3) diarrhea: high dose corticosteroids (2-4 mg/kg/day IV methylprednisolone) along with antibiotics; infliximab can be	Continue dosing Withhold the administration of CS1001 until resolved to $\leq$ Grade 1 Withhold the administration of CS1001 until resolved to $\leq$ Grade 1

Recurrent severe (Grade 3) or life- threatening (Grade 4): high dose corticosteroids (2-4 mg/kg/day IV methylprednisolone)		considered for steroid refractory diarrhea
high dose corticosteroids (2-4 mg/kg/day IV	discontinuation	
corticosteroids (2-4 mg/kg/day IV	from the study	threatening (Grade 4):
mg/kg/day IV		high dose
		corticosteroids (2-4
methylprednisolone)		mg/kg/day IV
along with antibiotics;		methylprednisolone)

irAE	Potential signs	Diagnosis and	Recommended	Dose modification
	and symptoms	differential	management	
		diagnosis	8	
			infliximab can be	
			considered for steroid	
			refractory diarrhea; in-	
			patient hospitalization	
			If bowel perforation is	Permanent
			suspected, steroid	discontinuation
			should be withheld,	from the study
			and surgical opinion	
			should be explored; in-	
			patient hospitalization;	
			Infliximab should not	
TT /'/'			be administered	W7.41.11.4
Hepatitis	Symptomatic:	Chemistry:	• Grade 2:	Withhold the
	fever, fatigue,	elevated levels	administration of	administration of
	nausea,	of hepatic transaminases	corticosteroids at a dose of 1-2	CS1001 until
	abdominal pain,			resolved to ≤ Grade 1
	hepatomegaly, Asymptomatic:	• Serologic	mg/kg/day	Glade I
	elevation of liver	testing: should	prednisone equivalents	
	function tests	be performed to rule out viral	-	
	(hepatic	hepatitis	• For subjects with liver metastasis or	
	transaminases,	(including	HCC who entered	
	bilirubin)	hepatitis A and	the study with	
		B),	Grade 2 elevation	
		cytomegaloviru	of AST/ALT,	
		s, and Epstein-	investigational	
		Barr virus	drug will be	
		Ultrasonograms	withheld if	
		of the liver	AST/ALT	
		Biopsy or	increase $\geq 50\%$	
		radiologic	relative to	
			baseline.	

1 1	imaging to		0 0 1	Democrat
		•	Severe ( $\geq$ Grade	Permanent
	distinguish		3): administration	discontinuation
	from other		of high dose	from the study
	etiologies of		corticosteroids (2-	
	hepatic injury,		4 mg/kg/day IV	
	such as		methylprednisolon	
	neoplastic		e); if not improved	
	disease		after 48-72 hours,	
	progression in		alternative	
	the liver,		immunosuppressi	
	infections, and		on agents	
	effects of other		(mycophenolate	
	medications or		mofetil) should be	
	alcohol intake		considered; in-	
			patient	
			hospitalization;	
			consultation with	
			a hepatologist	
		•	For subjects with	
			liver metastasis or	
			HCC who entered	

irAE	Potential signs	Diagnosis and	Recommended	Dose modification
	and symptoms	differential	management	
		diagnosis		
			the study with	
			Grade 2 elevation	
			of AST/ALT,	
			investigational	
			drug will be	
			permanently	
			discontinued if	
			AST/ALT	
			increase $\geq 50\%$	
			relative to	
			baseline and	
			lasting $\geq 1$ week	
			Total serum	
			bilirubin >3 times	
			upper limit of	
			normal	
Hypophysitis	Headache	Clinical	Grade 2 without	Withhold the
	refractory to	chemistry tests	adrenal crisis: high-	administration of
	nonsteroidal	• Endocrinologic laboratory test,	dose corticosteroids	CS1001 until
	anti-	ACTH, thyroid	(methylprednisolone 1	resolved to $\leq$
	inflammatory	function test,	to 2 mg/kg/day or the	Grade 1
	drugs or other	,	equivalent); initiate	
	analgesics;	Magnetic     resonance	appropriate hormone	
	weakness;		replacement therapy;	
	fatigue, weight	imaging (MRI) of the brain:	consultation with an	
	gain or weight		endocrinologist	D (
	loss; changes in	enlargement of the pituitary	Severe ( $\geq$ Grade 3) or	Permanent
	mood or	with variable	adrenal crisis: high-	discontinuation
	behavior;	contrast	dose corticosteroids	from the study
	hypotension;	enhancement	(methylprednisolone 1	
	electrolyte	characteristics	to 2 mg/kg/day or the	
	disturbances;		equivalent); consultation with an	
	abdominal pain;		endocrinologist	
	loss of libido;		chaochnologist	
	adrenal crisis;			
Nenhritis	hypogonadism Hematuria,	Clinical	Moderate (Grade 2):	Withhold the
Nephritis	peripheral	Clinical chemistry tests	administration of	administration of
		

Urine test

Biopsy if

	corticosteroids at a	CS1001 until
	edema, elevated serum creatinine			resolved to $\leq$
	serum creatinine	necessary	dose of 1-2 mg/kg/day	
		2	prednisone equivalents	Grade 1

			Severe (≥ Grade 3):	Permanent
			administration of	discontinuation
			corticosteroids at a	from the study
			dose of 1-2 mg/kg/day	
			prednisone equivalents	
Hypothyroidism	Typically	T3, T4, TSH test	Asymptomatic	Continue dosing
/hyperthyroidism	asymptomatic	results	Moderate (≤ Grade 2)	
	and is identified		hypothyroidism:	
	by lab tests		thyroxine replacement	
			therapy	
			Asymptomatic	Continue dosing
			Moderate (≤ Grade 2)	

irAE	Potential signs and symptoms	Diagnosis and differential	Recommended management	Dose modification
		diagnosis		
			hyperthyroidism: consider beta blockade	
			Severe ( $\geq$ Grade 3)	Withhold the
			hypothyroidism:	administration of
			replacement therapy	CS1001 until
				resolved to
				asymptomatic
				Grade 2 or $\leq$
				Grade 1 or baseline
			Severe (Grade 3)	Withhold the
			hyperthyroidism	administration of
			lasting $\geq 6$ weeks	CS1001 until
			despite active	resolved to
			management:	asymptomatic
			administration of	Grade 2 or <
			corticosteroids at a	Grade 1 or
			dose of 1-2 mg/kg/day prednisone equivalents	baseline
			Life-threatening (Grade 4) hyperthyroidism	Permanent discontinuation from the study
Dermatitis	Maculopapular	• Unless an	Moderate (≤ Grade 2,	Continue dosing
	rash or	alternative	up to 30% of body	6
	erythroderma,	etiology is	surface area): topical	
	pruritus, skin	identified, it	corticosteroids and	
	ulceration,	should be	oral over-the-counter	
	bullous	considered	antihistamines and	
	dermatitis,	immune-related	systemic	
	Stevens-Johnson	Pathologic	corticosteroids if no	
	syndrome	evaluation of	improvement within 7	
		skin biopsy can	days	
		be performed to	Severe (Grade 3, >	Withhold the
		rule out	30% of body surface	administration of
		alternative	area): administration	CS1001 until
		etiology	of corticosteroids at a	resolved to $\leq$
			dose of 1-2 mg/kg/day	Grade 2
			prednisone equivalents	

1	1		Life-threatening	Permanent
			e	
			(Grade 4, Stevens-	discontinuation
			Johnson syndrome,	from the study
			toxic epidermal	
			necrosis, full-thickness	
			dermal ulceration,	
			necrosis or	
			hemorrhage): high	
			dose corticosteroids	
			(2-4 mg/kg/day IV	
			methylprednisolone);	
			in-patient	
			hospitalization;	
			consultation with a	
			dermatologist	
Neuromuscular	Peripheral	Physical exam	Moderate (≤ Grade 2):	Withhold the
toxicity	sensory	~	administration of	administration of

irAE	Potential signs and symptoms neuropathy, muscle weakness, Guilliain-Barre syndrome, transverse myelitis,	Diagnosis and differential diagnosis of sensory change, loss of deep-tendon reflexes • Neuroimaging, nerve conduction	Recommended management corticosteroids at a dose of 1-2 mg/kg/day prednisone equivalents Severe (≥ Grade 3): high dose corticosteroids (2-4 mg/kg/day IV	Dose modification CS1001 until resolved to ≤ Grade 1 Permanent discontinuation from the study
	myasthenia gravis	exam, • Nerve/muscle biopsy	methylprednisolone)	
Ocular toxicity	Photosensitivity, pain or dryness of the eyes, blurred vision, uveitis, iritis, episcleritis	• ophthalmic exam	Moderate (≤ Grade 2): topical steroids (1% prednisolone) Severe (≥ Grade 3): high dose systemic corticosteroids (2-4 mg/kg/day IV methylprednisolone)	Withhold the administration of CS1001 until resolved to $\leq$ Grade 1; if not resolved $\leq$ Grade 1 within 14 days with topical steroids or initiation of systemic treatment, permanent discontinuation from the study Permanent discontinuation from the study
Other irAEs, such as arthritis, pancreatitis, hemolytic anemia, adrenal			Moderate (Grade 2)	Withhold the administration of CS1001 until resolved to $\leq$ Grade 1
insufficiency, myasthenic syndrome, and rhabdomyolysis			Severe (≥ Grade 3)	Permanent discontinuation from the study

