groups 3 mg/kg (2 subjects), 10 mg/kg (2 subjects), 20 mg/kg (2 subjects) and 1,200 mg fixed dose (7 subjects), respectively. 2 (6.9%) of these subjects reported increased conjugated bilirubin (in groups 3 mg/kg and 1,200 mg fixed dose, respectively), and the incidence of other AEs leading to delayed treatment cycle was 3.4%.

7 (24.1%) subjects experienced immune-related adverse reactions (irAEs), which occurred in groups 10 mg/kg (1 subject), 20 mg/kg (3 subjects) and 1,200 mg fixed dose (3 subjects), all of which were CTCAE grade 1 or 2 in severity. IrAEs with an incidence of  $\geq$  5.0% included hypothyroidism (13.8%) and pruritus (6.9%).

A total of 8 (27.6%) cases of death occurred during the study across all the groups, with the exception of group 20 mg/kg. 7 cases were due to the subject's disease, and 1 case with unknown cause. No subject died due to study treatment.

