## 6.4. STUDY TREATMRNT ADJUSTMENT

These guidelines should be followed by clinical Investigators, however, for an individual subject, dose interruptions, reductions, and treatment discontinuation should also be based on the clinical circumstance. Deviation from these guidelines must be documented and communicated with the sponsor. Adverse events are to be graded according to NCI CTCAE version 5.0.

- For the Phase Ib dose escalation, dose reductions for BLU-554 during the evaluation period of DLTs are only allowed if a DLT is observed.
- Dose reduction is not permitted for CS1001. If a subject experience a CS1001 related toxicities, then the subject must suspend or permanently discontinue CS1001 treatment.
- During the study treatment, if Investigator can judge AE is associated with one of the investigation products, the IP can be suspended, another IP could continue to be administrate. If cannot judge, both of the IPs should be suspended.
- If the study treatment is delayed according to the scheduled administration time for any reason (BLU-554 interrupted 2 weeks, CS1001 interrupted 9 weeks), the study treatment will no longer continue to be given (if the investigator considers that the subject is still benefiting, the subject may continue to receive the treatment with the consent of the medical monitor, i.e. the sponsor).
- Two administration delays are allowed due to toxicity. If the need for third delayed

administration of toxicity occurs, after consultation with the sponsor, the study treatment will be permanently terminated.

- 6.4.1. BLU-554 Dose Modifications
  - Any Grade 1 or Grade 2 BLU-554-related AE no dose modification required
  - Any Grade 3 or Grade 4 BLU-554-related AE, suspend (for at most 2 weeks) until event is ≤ Grade 1, or has returned to baseline, then resume by reducing 1 dose level. (if returned to ≤ Grade 1 or baseline within 14 days, and Investigator believes that it is in the subject's best interest, treatment may resume without dose reduction, with the written approval of the sponsor). If not resolved or returned to ≤ Grade 1 or baseline within 14 days, subjects should discontinue the treatment with BLU-554.
  - After reducing the dose of BLU-554 due to BLU-554-related adverse events, subjects should maintain such reduced dose during the subsequent treatment. The dose can be reduced as low as 300 mg.

\* In case immune mediated etiology cannot be excluded; consider following the guidelines in Section 14.3.

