6.4.2. CS1001 Dose Suspension

CS1001 will be **suspended** for any of the following CS1001-related adverse reactions:

- Any Grade  $\geq 2$  non-skin, drug-related adverse event, with the following exceptions:
  - Grade 2 drug-related fatigue or laboratory abnormalities do not require a treatment delay
  - Grade 2 drug-related hypothyroidism/hyperthyroidism do not require a treatment delay
- Any Grade 3 skin, drug-related adverse event
- Any Grade 3 drug-related laboratory abnormality, with the following exceptions:
  - Grade 3 lymphopenia does not require dose delay
  - For a subject who has Grade  $\geq 2$  drug-related AST, ALT, or total bilirubin elevation, dose delay is required
  - Any Grade ≥3 drug-related amylase or lipase abnormalities not associated with symptoms or manifestations of pancreatitis do not require dose delay. If such Grade ≥ 3 amylase or lipase abnormalities occur, the sponsor's medical monitor should be consulted
- Any adverse event, laboratory abnormality, or intercurrent illness which, in the judgment of the investigator, warrants delaying the dose of CS1001.

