6.6.3. Immune-Related Adverse Events

If an immune-mediated AE is suspected, the investigator should ensure that the evidence of etiology is conclusive or other causes may be excluded.

For any irAE of  $\geq$  Grade 3 or irAE of Grade 2 with the requirement of drug suspension or permanent withdrawal, the investigator should inform the sponsor as soon as possible and consult with the sponsor if necessary.

Based on the severity of AE, CS1001 will be suspended and corresponding treatment will be given. For subjects who use corticosteroids, corticosteroid dose will be gradually reduced within at least 1 month after the adverse reaction is improved to grade 1 or better. Short-term immunosuppressive agents such as tumor necrosis factor antagonists, mycophenolate mofetil or other drugs may be used if needed. If the severity of AE is maintained at grade 1 or better, CS1001 treatment can be restarted. In the event of an immune-mediated persistent, worsening or recurrent adverse event of Grade 3, or an immune- mediated event of Grade 4, CS1001 treatment should be discontinued permanently. For the identification, diagnosis, management and dose adjustment of irAE, please refer to APPENDIX 3: GUIDANCE FOR IMMUNE-RELATED ADVERSE REACTIONS MANAGEMEMT

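### Appendix 3 ties the CS1001 hold for Grade 3 hyperthyroidism to six weeks' duration, out of step with protocol 6.4.2, 6.4.4 and 6.6.3

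*Protocol*

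**What the plan says.** **Appendix 3 (14.3), hypothyroidism/hyperthyroidism row.** There are three hyperthyroidism entries.

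- Asymptomatic, up to Grade 2: "hyperthyroidism: consider beta blockade", with dosing continued.
- Grade 3 "lasting $\geq 6$ weeks" despite active management: corticosteroids, and CS1001 withheld until the event is asymptomatic Grade 2, Grade 1 or below, or baseline. (I read the lower limit as Grade 1 or below, as in the hypothyroidism entry.)
- Grade 4: permanent discontinuation.

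The neighbouring entry, hypothyroidism of Grade 3 or higher, withholds CS1001 with no duration condition.

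**6.4.2.** CS1001 is suspended for related non-skin events of Grade 2 or higher, with no minimum duration. The thyroid exemption is limited by grade: "Grade 2 drug-related hypothyroidism/hyperthyroidism do not require a treatment delay". A separate bullet suspends for "Any Grade 3 drug-related laboratory abnormality, with the following exceptions", and those exceptions do not include thyroid tests.

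**6.4.3.** CS1001 resumes at Grade 1 or below or at baseline. An endocrine exception covers events controlled with physiologic hormone replacement alone.

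**6.4.4.** CS1001 stops permanently for a related Grade 3 non-skin event that lasts more than 7 days. Exceptions include endocrinopathies controlled with physiologic hormone replacement alone, and most laboratory abnormalities.

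**6.6.3.** "Based on the severity of AE, CS1001 will be suspended and corresponding treatment will be given". Persistent, worsening or recurrent Grade 3 immune-mediated events lead to permanent discontinuation. The same section says: "For the identification, diagnosis, management and dose adjustment of irAE, please refer to APPENDIX 3".

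**The concern.** A site managing an immune-related thyroid event is directed to Appendix 3. Two features of the table invite the reading that CS1001 need not be held for Grade 3 hyperthyroidism until week 6. There is no entry for Grade 3 before six weeks, and the hypothyroidism entry next to it carries no duration condition, so the six-week qualifier looks deliberate. The qualifier may have been meant only for starting corticosteroids, but it heads the whole entry and so also conditions the dose-modification column.

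What is at stake is a dosing error: infusions given when 6.4.2 requires suspension, and possibly after the point at which 6.4.4 or 6.6.3 requires permanent discontinuation. No statement in the protocol says which text prevails.

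**Working it through.** The plan states no figure on this point, so the check compares the rules and then counts infusions.

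**1. The rules over time, for CS1001-related Grade 3 hyperthyroidism**

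| Time | 6.4.2 | 6.4.4 and 6.6.3 | Appendix 3 row |
|---|---|---|---|
| When identified | Suspend | 6.6.3: suspend by severity | Silent |
| After 7 days | Still suspended | 6.4.4: discontinue permanently unless an exception applies; 6.6.3: discontinue if persistent, worsening or recurrent | Silent |
| From 6 weeks | Still suspended | As above | Withhold, add corticosteroids, allow restart |

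Classing the event as a laboratory abnormality does not remove the conflict with 6.4.2, which also suspends at Grade 3 on that route. It does remove the 6.4.4 discontinuation, because the laboratory abnormalities that still require it are thrombocytopenia and liver tests. The hormone-replacement exception would not normally fit hyperthyroidism, because the event is hormone excess.

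The restart thresholds differ too. The row accepts asymptomatic Grade 2, while 6.4.3 asks for Grade 1 or below or baseline, subject to its endocrine exception.

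**2. Infusions that could fall in the six-week gap**

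Inputs:
- CS1001 every 21 days (synopsis, Study design).
- Appendix 3 trigger of 6 weeks = 42 days.
- Day 1 of Cycle 2 onward may move by ±4 days (schedule of activities, Tables 2 and 3).

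The count starts at recognition. An infusion given before the event is known would be given under 6.4.2 as well. Scheduled thyroid tests are at Cycles 1, 2, 4, 6 and so on, and the row itself describes these events as usually found by laboratory test.

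- Exact spacing, Grade 3 lasting the full 42 days: 42 / 21 = 2 infusions.
- Upper end with windows: doses due on days 0, 21 and 42 but given on days 4, 21 and 38 span 38 − 4 = 34 days, so 3 fit within 42. Four cannot, because their shortest span is 63 − 8 = 55 days.
- Lower end with windows: the same doses given on days −4, 21 and 46. A 42-day period starting on day −3 ends before day 39 and contains only the day-21 dose, so 1. The longest gap between doses is 21 + 8 = 29 days, so the count cannot be 0.
- Shorter Grade 3 events give fewer. With exact spacing the average is D/21 for D days at Grade 3 after recognition: 7/21 = 0.33, 14/21 = 0.67, 28/21 = 1.33.

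**3. Overlap with 6.4.4**

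The shortest gap between infusions is 21 − 8 = 13 days, so at most one can fall in the first 7 days. Unless an exception applies, any second or third infusion in the gap would breach 6.4.4 as well as 6.4.2.

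**4. How often**

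Among the 29 CS1001-101 Phase Ia subjects (2.4.1.2, Safety), 7 had immune-related events, "all of which were CTCAE grade 1 or 2 in severity". The earlier cut-off in 4.2.2 lists hyperthyroidism among immune-related events graded 1 to 3, but does not name it among its Grade 3 events. The row is therefore relevant, but its Grade 3 entry should rarely be needed.

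**The case against.** The strongest reply is that the protocol already gives the right answer. Section 6.4.2 is mandatory and exempts thyroid events only at Grade 2. Section 6.6.3, which refers sites to Appendix 3, itself suspends by severity and asks the investigator to inform the sponsor of any immune-related event of Grade 3 or higher. The appendix is titled guidance. A site reading all three would hold CS1001 when the event is identified. This stands, and it is why the point is minor. It does not remove the defect, because the table that sites are sent to for dose adjustment gives a trigger that matches none of the sections behind it. The footnote in 6.4.1 that asks investigators to "consider following the guidelines in Section 14.3" concerns BLU-554 and does not settle the force of the appendix for CS1001.

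Stronger readings are tempting, and the documents do not support them:

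- *The protocol instructs sites to keep dosing for six weeks.* It does not. The row is silent before six weeks. It gives an instruction to continue only for asymptomatic events up to Grade 2, and it does not claim to override 6.4.2.
- *Exactly two prohibited infusions per event.* The ±4-day windows, the length of the Grade 3 event and the time of recognition all move the count.
- *A predictable number of mis-dosed subjects.* The documents give no rate of Grade 3 hyperthyroidism on the combination and none for sites using the row alone.

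**Conclusion.** The point holds as a minor inconsistency in a safety instruction. The Appendix 3 entry sets its CS1001 hold later than 6.4.2 does, and it offers hold and restart at a stage when 6.4.4 and 6.6.3 would generally have ended CS1001 treatment.

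The size is about 2 infusions per event that stays at Grade 3 for six weeks after recognition, roughly 1 to 3 with visit windows, and fewer for shorter events. This assumes that the event is CS1001-related, that the site relies on the row alone, that the six weeks run from recognition, and that no other delay intervenes. The event is expected to be rare, and sponsor notification lowers the risk further.

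ORR, the analysis sets and the go/no-go criteria are unaffected. So is the DLT definition in 4.3.2, which counts immune-related events of Grade 3 or higher without a duration condition.

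**What to change.** Reword the Appendix 3 entry along these lines:

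> Grade 3 hyperthyroidism: withhold CS1001 when identified (per 6.4.2). Add corticosteroids, 1–2 mg/kg/day prednisone equivalent, if it persists despite active management. Permanently discontinue if 6.4.4 (more than 7 days, no exception applies) or 6.6.3 (persistent, worsening or recurrent Grade 3) is met. Otherwise resume per 6.4.3.

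In the same change, align the row's restart threshold (asymptomatic Grade 2) with 6.4.3: Grade 1 or below or baseline, with its endocrine exception.

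A general sentence that Section 6.4 governs would be the wrong repair. Appendix 3 is stricter elsewhere, for example on bilirubin (above 3 × ULN in the hepatitis row, against above 5 × ULN in 6.4.4) and on Grade 3 nephritis and hypophysitis, and such a sentence would loosen those rules.

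The cost is one table row reworded in the next amendment, with no change to visits, sample size or analysis.
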